2. LIST OF ABBREVIATION

AE Adverse Event

ADA Anti-Drug-Antibodies

ATC Anatomical Therapeutic Chemical classification system

AUC Area Under the Curve
BI Boehringer Ingelheim

BLRM Bayesian Logistic Regression Model

BMI Body Mass Index

BRPM Blind Report Planning Meeting

BSA Body Surface Area
CR Complete Remission
CTP Clinical Trial Protocol

CRi Complete Remission with incomplete marrow recovery

CLL Chronic Lymphocytic Leukaemia

CL Clearance

CTCAE Common Terminology Criteria of Adverse Event

CTh Concomitant therapies

DBL Database Lock

DILI Drug Induced Liver Injury
DLT Dose Limiting Toxicity

eCRF electronic Case Report Form

EOT End Of Treatment

FFS Failure Free Survival

G-CSF Granulocyte-Colony Stimulating Factor

ICH International Conference of Harmonization

IRR Infusion Related Reaction

IPV Important Protocol Violation

MedDRA Medical Dictionary for Regulatory Activities

MTD Maximum Tolerated Dose

MRT Mean Residence Time

NE Not Evaluable

OBD Optimal Biological Dose

O*C Oracle Clinical

PR Partial Remission

PD Progressive Disease

PFS Progression Free Survival

PK Pharmacokinetic

PKS Pharmacokinetic Set

PV Protocol Violation

PK/PD Pharmacokinetic/Pharmacodynamic

PT Preferred Term

REP Residual Effect Period

SAE Serious Adverse Event

SCR Screened Set

SD Stable Disease

SPD Sum of Product Diameter

SOC System Organ Class

SOP Standard Operating Procedure

TS Treated Set

TSAP Trial Statistical Analysis Plan

TLS Tumour Lysis Syndrome

UDAEC User-Defined Adverse Event Category

ULN Upper Limit of Normal

WBC White Blood Cell

WHO DD World Health Organisation Drug Dictionary

3. INTRODUCTION

As per International Conference of Harmonisation, statistical principles for clinical trials, E9 (ICH E9), the purpose of this document is to provide a more technical and detailed elaboration of the principal features of the analyses described in the Clinical Trial Protocol (CTP), and to include detailed procedures for executing the statistical analysis of the primary and secondary variables and other data.

This trial statistical analysis plan (TSAP) assumes familiarity with the protocol, including protocol amendments. In particular, the TSAP is based on the planned analysis specifications as written in CTP Section 7, "Statistical Methods and Determination of Sample Size". Therefore, TSAP readers may consult the CTP for more background information on the study, e.g., on study objectives, study design and population, treatments, definition of measurements and variables, planning of sample size. This TSAP follows the Boehringer Ingelheim (BI) internal guideline for developing a TSAP (1).

The primary objective of this trial is to determine the Maximum Tolerated Dose (MTD) or Optimal Biological Dose (OBD) of BI 836826 in patients with advanced chronic lymphocytic leukaemia. Secondary objectives are the collection of overall safety and anti-tumour efficacy data and the determination of the pharmacokinetic profile of BI 836826.

In the following, study medication always refers to BI 836826.

SAS® Version 9.4 (or higher) will be used for all analyses.

4. CHANGES IN THE PLANNED ANALYSIS OF THE STUDY

4.1 CLARIFICATIONS

As this trial is the first in human use of BI 836826, the primary objective as defined by the Clinical Trial Protocol (CTP) is to determine the maximum tolerated dose (MTD) of BI 836826. The MTD is determined via the number of dose limiting toxicities (DLTs). The CTP does not contain any definition of primary endpoint. But to follow the definition of the primary objective of the trial as defined by the CTP, the MTD and the number of patients with DLTs during the MTD evaluation period are defined as primary endpoints (see Section 5.1).

During the course of the trial it was decided to change the definition of some of the secondary and further endpoints:

1. Number of lymphocytes in the peripheral blood

The definition of this endpoint was changed from "Number of lymphocytes in the peripheral blood" to "Best % change from baseline in number of lymphocytes in the peripheral blood".

2. Blood counts (haemoglobin, platelets, neutrophils, red blood cells)

The definition of this endpoint was changed from "Blood counts (haemoglobin, platelets, neutrophils, red blood cells)" to "number of patients with improved haemoglobin count for at least two subsequent response assessments", "number of patients with improved platelet count for at least two subsequent response assessments" and "number of patients with improved neutrophil count for at least two subsequent response assessments". It was decided to abandon the definition of a separate secondary endpoint for red blood cells, since red blood cells are highly correlated with haemoglobin count and are thus reflected in this endpoint.

5. ENDPOINTS

5.1 PRIMARY ENDPOINTS

The primary objective of this study is the tolerability and safety of BI836826 as reflected by the MTD. Thus, primary endpoints of this trial are the MTD and the number of patients with DLTs during the MTD evaluation period. Instead of the MTD, an optimal biological dose (OBD) might be defined instead.

Maximum tolerated dose (MTD):

The MTD is defined as the highest dose studied for which the incidence of DLT is no more than 17% (i.e., 1/6 patients) during the MTD evaluation period.

The MTD evaluation period is defined as the duration of the first treatment course (i.e. 14 days after first administration of BI 836826).

For the definition of DLT please refer to the CTP Section 5.2.1.1. Please note that the definition of DLT was changed during the trial by amendments of the CTP. With CTP version 6 (04 March 2015), the following additional haematologic AEs were considered DLT:

- Grade 4 neutropenia lasting more than 7 days
- Febrile neutropenia not resolving within 48 hrs with appropriate treatment (antibiotics, antivirals, antifungals, growth factor support)
- Grade 4 thrombocytopenia lasting more than 7 days, or grade 3-4 thrombocytopenia with clinically significant bleeding
- Grade 4 anemia

The respective definition of DLT included in the CTP effective at the start time of the Adverse Event (AE) qualifying for a DLT was used.

5.2 SECONDARY ENDPOINTS

5.2.1 Key secondary endpoints

Not applicable.

5.2.2 Other Secondary endpoints

Note: For the response/efficacy analyses with respect to overall response assessment by investigator used: If patients would have their examinations contributing to the disease assessment over a number of days, the earliest date of the multiple examinations should be considered.

For the response/efficacy analyses with respect to lymphocytes and blood counts only laboratory data assessed >= 8 days after the last infusion and with reported laboratory response assessment on-treatment and before start of new Chronic Lymphocytic Leukaemia (CLL) therapy is used. The reason for this approach is that otherwise the respective values of lymphocytes and blood counts would be biased due to the infusion after which an immediate change in values of the respective blood parameters is observed. This change though does not reflect an efficacy effect.

Number of lymphocytes in the peripheral blood

The secondary endpoint with respect to number of lymphocytes in the peripheral blood is defined as "Best % change from baseline in number of lymphocytes in the peripheral blood".

Blood counts (haemoglobin, platelets, neutrophils)

The secondary endpoints with respect to blood counts are defined as

- "Number of patients with improved haemoglobin count for at least two subsequent response assessments"
- "Number of patients with improved platelet count for at least two subsequent response assessments"
- "Number of patients with improved neutrophil count for at least two subsequent response assessments"

An improvement is indicated by the fulfilment of the criteria for "Complete Remission" or "Partial Remission", i.e.

- Haemoglobin count: Greater than 11g/dL or increase of 50% or more compared to baseline if haemoglobin is less than or equal to 11g/dL
- Platelet count: Greater than 100 000/ μ L or increase of 50% or more compared to baseline if platelets are less than or equal to 100 000/ μ L
- Neutrophil count: Greater than 1500/ μL or increase of more than 50% compared to baseline if neutrophil count is less than or equal to $1500/\mu L$

Best overall response:

Response will be assessed according to the NCIWG guidelines (R10-4429) based on laboratory data from the peripheral blood and clinical examination by the investigator. Each patient will be assigned to one of the following categories:

- complete remission (CR)
- complete remission with incomplete marrow recovery (CRi)
- partial remission (PR)
- stable disease (SD)

- progressive disease (PD)
- not evaluable (NE)

Best overall response (CR, CRi, PR, SD, PD or NE in this order) is defined as the best overall response obtained since the start of study treatment until PD or start of next CLL therapy. Post-treatment assessments will be considered for the evaluation of best overall response as long as no further CLL therapy has started.

Progression free survival (PFS):

PFS is defined as the time from first treatment with BI 836826 until disease progression or death, whichever occurs first. A patient has an evaluable response assessment if either CR, CRi, PR, SD or PD has been assigned by the investigator.

Derivation of PFS is defined as PFS [days] = date of outcome – date of first administration of BI 836826 + 1.

The censoring rules and the applicable dates of outcome for PFS are given following table.

Table 5.2.2: 1 Derivation rules for progression-free survival

Situation	Outcome (event or censored)	Date of outcome
Disease progression or death	Event	Date of first disease progression or death
No disease progression or death without additional CLL therapy	Censored	Date of last response assessment
No disease progression or death with additional CLL therapy	Censored	Date of last response assessment before start of new CLL therapy
No baseline or post-baseline disease assessment and without death	Censored	Date of first administration of BI 836826
No baseline or post-baseline disease assessment and death on or before second planned disease assessment (i.e. 28 days after first administration of BI 836826)	Event	Date of death
No baseline or post-baseline disease assessment and death after second planned disease assessment (i.e. 28 days after first administration of BI 836826)	Censored	Date of first administration of BI 836826

Failure free survival (FFS):

FFS is defined as the time from first administration of BI 836826 until disease progression or death or start of next CLL therapy.

[figure not shown]
Derivation of FFS is defined as FFS [days] = date of outcome – date of first administration of BI 836826 + 1.

[figure not shown]
The censoring rules and the applicable dates of outcome for FFS are given in following table.

Table 5.2.2: 2 Derivation rules for failure-free survival

Situation	Outcome (event or censored)	Date of outcome
Disease progression or death or start of next CLL therapy	Event	Date of first disease progression or death or start of next CLL therapy
No disease progression, death or new CLL therapy	Censored	Date of last response assessment
No baseline or post-baseline disease assessment and without death or new CLL therapy	Censored	Date of first administration of BI 836826
No baseline or post-baseline disease assessment and death on or before second planned disease assessment (i.e. 28 days after first administration of BI 836826)	Event	Date of death
No baseline or post-baseline disease assessment and death after second planned disease assessment (i.e. 28 days after first administration of BI 836826)	Censored	Date of first administration of BI 836826

[figure not shown]

Proprietary confidential information © 2016 Boehringer Ingelheim International GmbH or one or more of its affiliated companies

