General safety laboratory parameters 	X	X	X	X	X	Х
Screening for Tumour Lysis Syndrome 	X	X				
Serum pregnancy test 	X				X	
_CMV monitoring 	X			 	x	X
			-			
		1				▏▋
End of active trial treatment					x	┣ ┛ ───
Outcome (remission, progression, death)					X	X
Other therapy for CLL						X

EOT: End of treatment, performed 14 days (± 2 days) after the last administration of BI 836826 FU: Follow-up, starts after EOT, visits at least every 4 weeks until 6 months after EOT, details see Section 6.2.3.2

CMV:

Cytomegalovirus HBV: Hepatitis B Virus

HCV: Hepatitis C Virus

Human Immunodeficiency Virus HIV:

\* the visit number follows the course number, i.e. visit 2 course 1 will read C1 V2 and visit 2 course 2 will read C2 V2 ...

\*\* the planned duration of a treatment course is 14 days

- 1 For AE assessment during FU refer to Sections 5.2.1 and Section 6.2.3.2
- 2 Concomitant therapy during FU only in case indicated for treatment of an AE (Section 4.2.1).
- 3 For details refer to Section 5.2.3.1
- 4 Screening for tumour lysis syndrome in between safety laboratory assessments (Section 5.2.3.2)
- 5 For women of childbearing potential only (please refer to Sections 3.3.3 (exclusion criterion 18) and 5.2.3.1)
- Quantitative CMV DNA PCR or pp65 antigen (Section 5.2.3.3.2) 6

Boehringer Ingelheim BI Trial No.: 1270.1		04 Mar 2015	
	568809-08	Trial Protocol	Page 7 of 111
8	prior to starting treatmen	nent (peripheral blood, clinical) has to be perfo nt, and at day 1 of subsequent courses prior to t ed 1 day earlier to allow for a timely continuation reatment administration.	he next administration of BI
9			

If patients continue beyond cycle 8 in agreement with investigator and BI, the same assessments will be done as applicable for cycle 5-8.

[figure not shown]

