6. GENERAL ANALYSIS DEFINITIONS

6.1 TREATMENTS

In this Phase I trial, treatments are not randomised (open-label, dose escalation). Different dose levels of BI 836826 are being administered. The data will be presented for all dose cohorts separately and in total over all dose cohorts. To justify the MTD determination, DLTs occurring during the MTD evaluation period (during the first treatment course) will be presented separately from those occurring during the complete on-treatment period.

"Analysing treatment" will be used for reporting of treatment emergent adverse events (AE) and to differentiate between screening, on-treatment, post-treatment and post-study safety data. The inequalities start date \leq onset date of AE < end date will determine whether the AE will be assigned to the "analysing treatment" or not. Table 6.1:1 defines the "analysing treatment period" which will be used for reporting of treatment emergent AEs and safety laboratory parameters. Safety data recorded during the Residual Effect Period (REP) will be considered as on-treatment.

If not specified otherwise, all safety tables will be based on the on-treatment period. AEs that have an onset date during the screening or post-study periods will be displayed in separate listings from those occurred during the on-treatment period.

T 11 (1	1 D C '.'	C 1 .		. 1()
Table 6 1:	I Definition	of analysing	treatment	neriodist
I dolo o.i.	1 Dominion	OI unui yonii 🗲	, u cuuniciit	periodisi

Analysing treatment period	Start date (including)	Stop date (excluding)	
Screening	Date of informed consent	Date of first administration of study medication	
On-treatment	Date of first administration of study medication	Start date of 'Follow-up'	
Follow-up	Date of end of REP +1	Start date of 'Post-study'	
Post-study	Last date patient status obtained / last date patient known to be alive + 1 (if patient is lost to follow-up) / date of refusal + 1 day / the date patient died + 1	During the trial: open / empty; after database lock (DBL): DBL + 1 day	

The initial study medication assigned at the beginning of the first treatment course will be used as the label of the analysing treatment.

The actual dose of study medication administered on the day each AE started will also be derived. This will be presented in patient listings, but will not be used for defining treatments for analysis.

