7.8.1.2 Adverse events

Unless otherwise specified, adverse events analysis will be performed for on-treatment periods. Selected analyses (e.g. summary of AEs) will be repeated for the MTD evaluation period.

The analyses of AEs will be descriptive in nature and will follow the standard procedure laid down in the DM & SM (including all required tables and listings; guideline _'Handling and Summarization of AE Data for CTR and Integrated Summaries' (4). AEs will be coded with the most recent version of Medical Dictionary for Regulatory Activities (MedDRA). The version number will be displayed as a footnote in the respective tables and listings.

The system organ classes will be sorted alphabetically. In tables displaying AEs by dose cohort preferred terms will be sorted by descending frequency of adverse events in the "Total" BI 836826 group.

Each patient can be observed during the trial under several doses. Analysing the AE of all treatment courses will be carried out under the initial treatment. No formal statistical analysis is planned for the safety comparison.

The analysis of AEs will be based on the concept of treatment emergent AEs. That means that all adverse events occurring between first administration of BI 836826 until 6 weeks after last administration of BI 836826 will be assigned to the on-treatment period. All adverse events occurring before first administration of BI 836826 will be assigned to "Screening" and all adverse events occurring after last administration of BI 836826 + 6 weeks will be assigned to "post-study (for listings only). The actual planned dosage of BI 836826 administered on the day each AE starts will also be derived and will be included in the listing. Listings of screening events will not be sorted by initial treatment. Post-study listings will be sorted by initial treatment. For details on the treatment definition please refer to Section 6.1.

According to the BI standards, multiple recordings of AEs will be collapsed to episodes on the lowest level term and multiple episodes will be condensed to records on the PT and system organ class (SOC) level. CTCAE grade will be an additional criterion for collapsing and condensing AEs. The maximum CTCAE grade will be assigned to episodes and records. CTCAE grade and DLT information will be displayed in AE listings. MedDRA levels for condensing will be SOC and PT.

An overall summary of adverse events will be presented.

Reporting of CTCAE grades

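### The haemoglobin, platelet and neutrophil improvement endpoints have no stop at progression, although the lymphocyte endpoint and best overall response do

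*SAP*

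**What the plan says.** SAP 5.2.2 applies one filter to the lymphocyte and blood-count endpoints together. Its first part sets a minimum distance from dosing: "only laboratory data assessed >= 8 days after the last infusion". Its second part sets the observation window: "with reported laboratory response assessment on-treatment and before start of new Chronic Lymphocytic Leukaemia (CLL) therapy is used". The haemoglobin endpoint is "Number of patients with improved haemoglobin count for at least two subsequent response assessments", and the platelet and neutrophil endpoints follow the same pattern. Improvement means meeting the count criterion for complete or partial remission. SAP 7.5.2 then specifies a frequency table on the Treated Set and gives no further time limit for these three endpoints.

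Two neighbouring endpoints are bounded differently. Best overall response is the "best overall response obtained since the start of study treatment until PD or start of next CLL therapy", and SAP 5.2.2 adds: "Post-treatment assessments will be considered for the evaluation of best overall response as long as no further CLL therapy has started". For lymphocytes, SAP 7.5.2 ends the best percentage change at subsequent CLL therapy or PD.

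The on-treatment period is described in the safety sections. SAP 7.8.1.2 says that adverse events "until 6 weeks after last administration of BI 836826 will be assigned to the on-treatment period". In SAP Table 6.1:1 the Follow-up period begins at "Date of end of REP +1", where REP is the residual effect period. The protocol flow chart has "Follow-up, starts after EOT, visits at least every 4 weeks until 6 months after EOT".

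**The concern.** An endpoint built from remission criteria should not credit a patient with improvement on the strength of an assessment made after the disease has progressed. The SAP prevents this for lymphocytes and for best overall response, but not for the three blood-count endpoints. PD can be declared on nodes, liver, spleen or lymphocytes while haemoglobin, platelets and neutrophils remain adequate. A patient can therefore have progressed and still meet the count criterion at a later visit.

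At stake is the reading of three named secondary endpoints by dose cohort. Some patients listed as improved could owe that status to a value taken after PD, and the same report would treat that visit as out of bounds for the other two endpoints.

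**Working it through.** **Step 1. The stopping rules side by side (SAP 5.2.2 and 7.5.2).**

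| Endpoint | Stops at PD | Stops at new CLL therapy | Limited to on-treatment | 8-day rule |
|---|---|---|---|---|
| Haemoglobin, platelet, neutrophil improvement | not stated | yes | yes | yes |
| Lymphocytes, best % change | yes (7.5.2) | yes | yes (shared filter) | yes |
| Best overall response | yes | yes | no, post-treatment included | no |

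The lymphocyte and blood-count endpoints share the filter. What separates them is the missing PD stop.

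**Step 2. Can values after PD exist inside the window?** Protocol 6.2.3.2 ends follow-up at loss to follow-up, at new anti-neoplastic therapy, or when investigator and sponsor agree to stop. PD is not on that list. Safety laboratory and response assessment are both listed for follow-up visits. Protocol 5.1.2.4.4 does not allow cytopenia to define progression during therapy, so PD on other criteria can coexist with adequate counts.

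**Step 3. Worked case.** Inputs: EOT 14 days after the last dose (protocol 6.2.3.1), first follow-up 4 weeks later (6.2.3.2), PD found at EOT, no new CLL therapy, counts adequate at both visits.

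- EOT: day 14. 14 ≥ 8, on-treatment: eligible.
- First follow-up: 14 + 28 = day 42. 42 ≥ 8, and within 6 × 7 = 42 days: eligible if the 6-week period applies.
- Eligible improved assessments: 2. The patient counts as improved, and the second assessment is 28 days after PD.
- With a PD stop, the day-42 value drops out. At most one of the two remains, so this pair no longer qualifies. A patient with two improved assessments before PD is unaffected.

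**Step 4. Secondary check: where the window ends.** This assumes that the safety definition of on-treatment governs the efficacy filter. The residual effect period is 6 × 7 = 42 days, which matches the 42 days in protocol Table 5.2.2.2:1. Follow-up then starts on day 43 and the on-treatment stop date is exclusive, so the last included day is 42.

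First follow-up day = EOT day + 28, with EOT at 14 ± 2:

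| EOT day | First follow-up day | Inside window |
|---|---|---|
| 12 | 40 | yes |
| 13 | 41 | yes |
| 14 | 42 | yes, no slack |
| 15 | 43 | no |
| 16 | 44 | no |

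Eligible assessments through EOT, with course 1 given on days 1 and 2, equal the number of courses. One more is added if the first follow-up falls by day 42:

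| Courses | Through EOT | With first follow-up |
|---|---|---|
| 1 | 1 | 2 |
| 2 | 2 | 3 |
| 4 | 4 | 5 |
| 8 | 8 | 9 |

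On the four-weekly schedule, a one-course patient can reach the required two only if that visit is in. If course 1 is split over days 1, 2 and 8, the assessment before course 2 on day 15 is 15 − 8 = 7 days after infusion and fails the 8-day rule. A two-course patient then also has 1 or 2.

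**The case against.** The endpoints are descriptive, the protocol plans no formal tests (7.2), the primary objective is the MTD, and mean counts over time are plotted as well. That is right, and it limits the weight of the point.

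Best overall response is not a like-for-like comparator. Partial remission needs two group A criteria and one group B criterion held for at least 2 months (protocol 5.1.2.4.3), whereas two subsequent assessments can be about 14 days apart. This stands as a reason why the two windows need not match in length. It gives no reason to accept values after PD, and the lymphocyte endpoint, which shares the filter, does stop there.

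In the ordinary case PD is found at EOT, so only one of the two qualifying visits comes after PD. That is correct, and it is the case worked above. Two visits after PD would need PD found mid-course or treatment continued beyond it. It is also possible that no laboratory response is recorded after PD, in which case the filter would exclude the value. The documents do not say so, and protocol 5.1.2.4 calls for response assessment at all follow-up visits.

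A reader might go further and infer that the on-treatment limit is itself an error which discards lasting improvement. The documents do not support that:

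- Protocol 5.1.2.3 speaks of improvement during therapy, so the limit fits the protocol.
- Two improved on-treatment assessments suffice, however long the improvement lasts. Only improvement that starts late, or whose second assessment falls outside the window, is at risk.
- It cannot be said that every later follow-up visit is lost or that improvement first seen in follow-up can never qualify. Protocol 3.2 and 6.2.3.2 allow earlier or more frequent visits, so two could fall by day 42, for example on days 28 and 42.
- SAP Table 6.1:1 and 7.8.1.2 are worded for adverse events and safety laboratory data. Day 42 as the end of this efficacy window is an inference.

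**Conclusion.** The point holds for the missing PD stop. The SAP states none for the three blood-count endpoints in either 5.2.2 or 7.5.2, and a value after PD can complete the pair needed for improvement. The worked case rests on PD at EOT, no new therapy, a first follow-up visit by day 42 with a reported laboratory response, and the 6-week reading of on-treatment. If on-treatment ended at EOT, no follow-up visit would count, and the case would arise only with PD before EOT.

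The dependence on day 42 is secondary and conditional on that same reading. One or two days of allowed scheduling decide whether the first follow-up visit counts, which matters mainly for one-course patients. How many patients either point would reclassify cannot be computed from the documents.

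**What to change.** In SAP 5.2.2, for the haemoglobin, platelet and neutrophil endpoints, make the stopping clause read *before PD or start of new CLL therapy*. Keep the 8-day rule and the on-treatment limit. State whether an assessment on the date of PD itself is eligible, and repeat the window in the blood-count paragraph of 7.5.2. The cost is one clause and one date condition on data already collected. The downside is that a few patients with PD may no longer qualify.

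Also say which definition of on-treatment applies to this filter, and set the last eligible assessment by visit (for example EOT or the first follow-up visit) rather than by day.

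Using all follow-up visits until PD or new therapy is optional and at most a supplementary analysis. After EOT only concomitant therapy for an adverse event is reported (protocol 4.2.1), while the partial-remission count criteria exclude growth factors (all three counts) and transfusions (platelets and haemoglobin). Recovery from drug-induced cytopenia could also be read as improvement.
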